Humalog U-200 KwikPen is a prefilled and multi-dose pen-injector device (pen) that delivers insulin lispro by subcutaneous injection to improve glycemic control in adults and children with diabetes mellitus. Compared to Humalog U-100 KwikPen, it contains the same number of units of insulin lispro in half the volume. Despite warning messages on the pen and in the instructions for use, results from Human Factors studies performed in the United States (US) showed that a small percentage of patients may choose to withdraw insulin from the pen cartridge with a syringe if faced with device malfunction. Anecdotal information also indicates that patients may transfer insulin lispro from the pen cartridge into an insulin pump. Because of these data and to further optimize the benefit-risk balance of the presentation, additional Risk Minimization Measures beyond routine risk minimization measures (are being implemented, including communications to Healthcare Professionals (HCPs) and patients to minimize the risk of hyperglycemia and/or potentially hypoglycemia associated with insulin transfer from the pen cartridge to an alternative administration device without concentration adjustment and dose adjustment when transferring from Humalog U-100 KwikPen to Humalog U-200 KwikPen.

The additional Risk Minimization Measures will include a Direct Healthcare Professional Communication (DHPC) that will be distributed to pharmacists and prescribers (endocrinologists and mealtime insulin prescribing primary care physicians, nurse practitioners, and physician's

assistants). A patient communication document will be distributed in the single pen product sample packages that are routinely provided by HCPs to patients who have been newly prescribed Humalog U-200 KwikPen.

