- Extent of understanding of the key safety messages for Humalog U-200 KwikPen, as communicated through risk minimization measures (Were the key safety messages in the patient communication understood by the patient?)
- Extent of recall/receipt of the patient communication in the patient sample upon first prescription of Humalog U-200 KwikPen (Does the patient recall receiving the patient sample which included the patient communication document?)
- Extent of key safety message consideration by patients during administration of Humalog U-200 KwikPen (Will the patient follow the key safety messages communicated during administration of Humalog U-200 KwikPen?)

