5.4.1. Inclusion criteria

HCPs must meet the following criteria to be eligible for inclusion in the survey:

- HCPs are aware of the insulin product Humalog U-200 KwikPen; and
- HCPs are involved in the treatment and management of patients with diabetes.

Patients must meet all of the following criteria to be eligible for inclusion in the survey:

- Patients are 18 years or older;
- Patients have diabetes; and
- Patients have filled at least one (1) prescription of Humalog U-200 KwikPen within the past 90 days.

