- Self-reported practices with respect to communication of the key safety messages in clinical practice

Patients:

Screening questions:

- Agreement to participate
- Diagnosis of diabetes
- Filled a prescription for Humalog U-200 KwikPen within the past 90 days prior to survey launch
- 18 years or older
- Employment by Lilly, UBC, or the FDA

Data on demographic characteristics:

- Age
- Gender
- State
- Employment status
- Length of time with diabetes
- Length of time on any insulin therapy
- Length of time on Humalog U-200 KwikPen
- Length of time on mealtime Insulin used prior to Humalog U-200 KwikPen

Data pertaining to evaluation of the effectiveness of the risk minimization measures:

The survey includes questions/statements that will assess the risk understanding and behavior of patients. The understanding level and behaviors will be analyzed using descriptive statistics and CIs and will be used to determine the effectiveness of the risk minimization measures:

- Awareness of the Important Safety Information for Humalog U-200 KwikPen
- Receipt of or access to the Important Safety Information
- Understanding of the key safety messages
- Behavior with respect to the key safety messages

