[BEGIN PREAMBLE 2 – DISPLAY ON SAME PAGE AS NEXT QUESTION]

The following questions are about Humalog® U-200 KwikPen®.

[END PREAMBLE 2]

15. Please answer True, False, or I don't know for each of the following statements regarding Humalog® U-200 KwikPen®.

	[RANDOMIZE LIST]	True	False	I don't know
A	Humalog® U-200 KwikPen® is approved for transfer to syringe or pump.			
B	The dose of insulin does not need to be converted when changing patients from one Humalog strength to the other (for example, changing a patient from Humalog U-100 units/mL to Humalog® U-200 KwikPen®).			
C	When prescribing Humalog® U-200 KwikPen®, it is important to clearly indicate the correct strength on the prescription.			
D	It is important to instruct your patients that they should always have a backup pen available.			

16. Are you aware of the Direct Healthcare Professional Communication provided to you by Eli Lilly and Company on the correct use of Humalog® U-200 KwikPen® (*insulin lispro*) to minimize medication errors?

- Yes
- No **[GO TO Q18]**
- I don't know **[GO TO Q18]**

17. Did you read the Direct Healthcare Professional Communication provided to you by Eli Lilly and Company on the correct use of Humalog® U-200 KwikPen® (*insulin lispro*) to minimize medication errors?
- Yes
 - No
 - I don't know
18. Are you aware of the patient communication Patient Information Letter/*IMPORTANT SAFETY INFORMATION FOR* Humalog® U-200 KwikPen® (*insulin lispro*) that is included in patient sample packs of Humalog® KwikPen® provided by Eli Lilly and Company?
- Yes
 - No **[GO TO Q20]**
 - I don't know **[GO TO Q20]**
19. Have you read the patient communication: Patient Information Letter/*IMPORTANT SAFETY INFORMATION FOR* Humalog® U-200 KwikPen® (*insulin lispro*) provided by Eli Lilly and Company?
- Yes
 - No
 - I don't know

[DO NOT DISPLAY QUESTION 20 IF 0 IS SELECTED IN QUESTION 11]

20. Do you or another healthcare professional at your practice discuss the safe use of the Humalog® U-200 KwikPen® to patients receiving their initial prescription?
- Yes
 - No
 - I don't know

[DO NOT DISPLAY QUESTION 21 IF 0 IS SELECTED IN QUESTION 11]

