	[RANDOMIZE LIST]	True	False	I don't know
A	Humalog® U-200 KwikPen® should only be injected using the prefilled KwikPen device in which it is supplied.			
B	Your dose of insulin does not need to be converted when changing from one strength of Humalog to the other (for example, changing from Humalog U-100 KwikPen to Humalog® U-200 KwikPen®).			

16. Please answer Yes, No, or I don't know for each of the following statements about the Patient Information Letter/*IMPORTANT SAFETY INFORMATION FOR* Humalog® KwikPen®, 200 units/mL, U-200 *insulin lispro* injection.

[RANDOMIZE LIST]		Yes	No	I don't know
A	The first time I was prescribed Humalog® U-200 KwikPen®, my doctor or nurse provided me with a paper copy of the Patient Information Letter/ IMPORTANT SAFETY INFORMATION . (This letter was included with the patient sample pen pack.)			
B	My doctor or nurse offered to explain information about the safe use of Humalog® U-200 KwikPen® the first time I was prescribed this product.			
C	I think about the important safety information for Humalog® U-200 KwikPen® to remind myself of the risks when injecting my insulin.			
D	I should always have a backup pen with me.			
E	It is ok to transfer insulin from the pen using a syringe.			

17. Other than the information you have received from your doctor or nurse, from what sources have you received and/or accessed information on the safe use and understanding of the Humalog® U-200 KwikPen®. (Please select all that apply.)

[RANDOMIZE LIST – KEEP OTHER AT THE BOTTOM]

- Pharmacist
- Other Healthcare Professional
- Diabetes Support Group
- Internet
- Product Warning Label
- Other

[TELEPHONE: BEGIN SAFETY EVENT/PRODUCT COMPLAINT – KEEP ON ONE PAGE]

(INTERVIEWER: Please record if respondent spontaneously reported a safety event or product complaint during the course of this interview.)

- Yes
- No **[GO TO CLOSING 1]**

Enter Safety Event or Product Complaint Verbatim

[MULTILINE INPUT]

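### The patient survey measures recalled hand-over of the letter by a doctor or nurse, but has no item for sample receipt, awareness of the letter, or receipt by another route, although these are stated outputs

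*Protocol*

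**What the plan says.** **Stated outputs.** Section 4 lists, for patients, "Extent of recall/receipt of the patient communication in the patient sample upon first prescription of Humalog U-200 KwikPen", and spells it out as "Does the patient recall receiving the patient sample which included the patient communication document". Section 5.6 lists "Awareness of the Important Safety Information for Humalog U-200 KwikPen" and, as a separate line, "Receipt of or access to the Important Safety Information". Section 5.9 repeats both among the results to be reported.

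**How the letter reaches patients.** Section 3.1: "A patient communication document will be distributed in the single pen product sample packages that are routinely provided by HCPs to patients". The recipients meant are those newly prescribed the product.

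**Who is surveyed.** Section 5.4.1: "Patients have filled at least one (1) prescription of Humalog U-200 KwikPen within the past 90 days". Having received a sample is not a condition.

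**The item.** Appendix I.3, Q16A, states that at first prescription a doctor or nurse supplied a paper copy of the letter, followed by the bracketed sentence "This letter was included with the patient sample pen pack". There is one response: Yes, No or I don't know. The patient correct-answer document prints the same sentence without brackets and gives Yes as the correct response.

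**How non-receipt is read.** Section 5.11 says that when a respondent reports not getting the communication, the programme is judged to have distributed it less than optimally. It also acknowledges that the respondent may simply have forgotten.

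**The HCP survey.** Appendix I.1 has separate awareness and reading items for the HCP letter (Q16, and Q17: "Did you read the Direct Healthcare Professional Communication provided to you by Eli Lilly and Company") and for the patient letter (Q18 and Q19).

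**The concern.** The questionnaire fixes which data will exist. If a stated output has no item behind it, no later analysis plan can supply it. Here one item has to carry receipt of the sample, awareness of the letter, and receipt of or access to the letter.

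What is at stake is how a low rate is interpreted. If few patients recall the letter, the sponsor needs to know which step failed. Samples may not be reaching newly prescribed patients, or they may be reaching them with the letter going unnoticed. The first is a fault of the distribution route and the second a fault of the communication. They call for different corrective action, and Q16A returns the same 'No' for both.

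**Working it through.** **Step 1. Match the stated outputs to the patient items (Appendix I.3, Q1 to Q17).**

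| Output | Stated in | Direct item |
|---|---|---|
| Recall of receiving the sample | Section 4 | none |
| Awareness of the letter | Sections 5.6, 5.9 | none |
| Receipt of the letter from a doctor or nurse | Sections 4, 5.6, 5.9 | Q16A |
| Receipt of or access to the letter by another route | Sections 5.6, 5.9 | none |
| Reading the letter | not a stated patient output | none |

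The neighbouring items do not fill the gaps. Q16B concerns an offer to explain safe use. Q16C asks whether the patient thinks of the safety information when injecting, which presupposes awareness. Q17 asks about sources other than the doctor or nurse and offers neither the letter nor the sample pack as an option.

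**Step 2. What each Q16A answer establishes.** Taken at face value, 'Yes' means recalled hand-over and implies awareness, so the 'Yes' rate is a floor for awareness. 'No' fits at least three situations: no sample was given; a sample was given and the letter was not noticed; or the patient found the letter in the pack and does not count that as being given it by the doctor or nurse. 'No' does not establish lack of awareness.

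**Step 3. The plan's own precision.** Section 5.7, Equation 1: half-width = 1.96 × √[p(1 − p)/n]. At p = 0.50 and n = 280 this is 1.96 × √(0.25/280) = 5.86 points, which matches the 5.9 in Table 1. The other four rows also reproduce (5.74, 5.37, 4.69 and 3.51 points). The table is not in dispute.

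**Step 4. Illustration of what is not identified.** The documents do not say what share of patients receives a sample, so the following inputs are assumptions. Let the Q16A 'Yes' rate be 45% of 280. Its 95% CI is 45 ± 1.96 × √(0.45 × 0.55/280) = 45 ± 5.8, or 39.2% to 50.8%. Assume also that the letter reaches patients only through the sample. Then letter receipt given a sample = 0.45 / (share with a sample):

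| Assumed share with a sample | n with a sample | Letter receipt given a sample |
|---|---|---|
| 45% | 126 | 0.45/0.45 = 100% |
| 50% | 140 | 0.45/0.50 = 90% |
| 75% | 210 | 0.45/0.75 = 60% |
| 100% | 280 | 0.45/1.00 = 45% |

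The same observed rate fits anything from 45% to 100%. A larger survey would narrow the CI around 45% but not this range.

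**Step 5. Precision with a sample item.** Among those recalling a sample, the worst-case half-width (p = 0.50) is 1.96 × √(0.25/140) = 8.3 points at n = 140 and 1.96 × √(0.25/210) = 6.8 points at n = 210, against 5.9 at n = 280.

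**The case against.** The best defence is that Q16A follows the Section 4 output closely: first prescription, a paper copy, a doctor or nurse, and the sample pack named. The documents describe one distribution route, so the bracket can be read as a recall cue, not a second question. 'I don't know' is offered to anyone unsure, and Section 5.11 already admits that recall is imperfect.

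Much of this stands. Q16A gives a usable rate, with a CI, for recalled hand-over. A reader might infer that the receipt question cannot be answered at all; that goes too far. The defence does not, however, supply an item for the sample or for awareness. The correct-answer document also weakens the recall-cue reading, because it prints the sample-pack sentence as part of the statement.

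Other stronger readings are tempting and are not supported:

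- **That ambiguity in Q16A could tip the effectiveness verdict across a 50% line.** The majority criterion in Section 5.3 concerns the key safety messages. Its patient bullets are understanding them and following them, not receipt of the letter.
- **That comparisons of understanding by exposure will be misclassified.** Sections 5.7 and 5.9 plan no such comparison. The only subgroup analysis named is HCPs by specialty.
- **That the missing reading item leaves a stated question unanswered.** Reading is not a patient output in Sections 4, 5.6 or 5.9. Its absence is an asymmetry with the HCP survey and no more.
- **That a numerical bias in the Q16A rate can be quoted.** The documents give neither the share of patients receiving a sample nor the share noticing the letter.

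**Conclusion.** The point holds in a limited form. The patient survey covers part of its receipt output and has no direct item for two things the protocol says it will learn: recall of the sample and awareness of the letter. Receipt or access by a route other than the doctor or nurse is also not captured. Because patients enter on filled prescriptions and the letter travels in samples, a 'No' to Q16A cannot distinguish a patient who got no sample from one who overlooked the letter. Section 5.11 would count both as a distribution shortfall.

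The size cannot be fixed from the documents. In the illustration, a 45% 'Yes' rate is compatible with letter receipt among sample recipients anywhere from 45% to 100%. That rests on the assumed 45% and on the sample being the only route. The understanding endpoints and the precision table are unaffected. The change is worth making because what is not asked cannot be recovered after data collection.

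**What to change.** Replace Q16A with separate items, each answered Yes, No or I don't know:

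1. received a sample pack of the product when first prescribed it;
2. aware of the Patient Information Letter;
3. received the letter, in the sample pack or otherwise;
4. optionally, read the letter, as the HCP survey asks of HCPs.

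Report receipt of the letter overall and among those who recall a sample, and report awareness as its own line so that Sections 5.6 and 5.9 are met. Amend Section 5.11 so that reported non-receipt is interpreted separately for those with and without a recalled sample.

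Do not score these items as correct or incorrect, and take Q16A out of the patient correct-answer document. They are questions of fact about the patient's history. If the Section 5.9 rule that treats I don't know as incorrect were applied to them, failure to recall would merge with non-receipt.

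**Cost.** A few short closed items in a survey of about 15 minutes, minor reprogramming and an IRB notice. The estimate among sample recipients has a smaller denominator: at worst about 8.3 points half-width if half of the 280 recall a sample, or 6.8 points if three quarters do.

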5.11. Limitations of the research methods

The participants will be self-selected since they will voluntarily respond to the invitation to participate. The survey recruitment strategies will include a random sample of HCPs who received educational outreach, which should be generalizable to the overall HCP population who are educated about the use of Humalog U-200 KwikPen.

Patients will be recruited via the PBM database and will be identified as those patients who have filled/refilled a prescription for Humalog U-200 KwikPen.

Additionally, inherent in survey research is the reliance on the respondent's recall for whether or not the risk minimization communication was received in order to evaluate the scope of risk minimization measures. If the respondent says she/he did not receive the communication, the risk minimization program is evaluated as not optimally disseminating material. It is possible, however, that respondents may simply not recall receiving the tools that were, in fact, received. It is also possible that they have acceptable understanding of the risks and appropriate behaviors despite not receiving or recalling receipt of the risk minimization measure-specific communication. All data from the survey are self-reported and therefore susceptible to possible reporting bias. This is also applicable to the patients' self-reporting of their practice behaviors to minimize the risks. There may be discrepancies between what respondents report about their practices and their actual behaviors.

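### Patient item 16A asserts that the letter came with the sample pack, so a 'Yes' cannot separate recall of the letter from inference, and reported receipt may be overstated by an unknown amount

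*Protocol*

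**What the plan says.** - **Research question.** Protocol section 4 lists for patients "Extent of recall/receipt of the patient communication in the patient sample upon first prescription of Humalog U-200 KwikPen" and glosses it as "Does the patient recall receiving the patient sample which included the patient communication document".
- **Reported result.** Section 5.6 lists "Receipt of or access to the Important Safety Information", next to a separate entry for awareness, among the data used to judge the risk minimization measures. Section 5.9 repeats both for reporting.
- **The item.** Q16 in Appendix I.3 opens with "Please answer Yes, No, or I don't know for each of the following statements about the Patient Information Letter". Statement A says that the doctor or nurse supplied a paper copy at the first prescription, and adds in brackets "This letter was included with the patient sample pen pack".
- **The key.** The patient correct answer document at the end of Appendix I.3 gives 'Yes' as the correct response to 16A.
- **Distribution.** Section 3.1: "A patient communication document will be distributed in the single pen product sample packages that are routinely provided by HCPs". No other route to patients before the survey is described.
- **Sampling.** Section 5.11: "Patients will be recruited via the PBM database and will be identified as those patients who have filled/refilled a prescription". Having been given a sample is not an entry condition.
- **Limitations.** Section 5.11 says that "respondents may simply not recall receiving the tools that were, in fact, received". It also warns in general terms that all the data are self-reported and open to reporting bias.

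**The concern.** A question on receipt should not tell the respondent where the thing was. A patient who remembers a sample pack, or some paper supplied with a pen, can reason from the bracketed sentence to 'Yes' without remembering the letter. A patient who never had a sample may be nudged the same way.

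Nothing else in the survey would show this. Item 16C asks about thinking of the safety information when injecting, and Q17 asks about sources other than the doctor or nurse; neither asks whether the letter arrived. Prescribers get separate questions on awareness and on reading of the communications, but their answers are not linked to patients. The key makes matters slightly worse: receipt is personal history with no right answer, and a patient who truthfully says 'No' is told that this was incorrect.

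At stake is the reading of the dissemination result. A high 'Yes' rate could mean that the letter reached patients, or partly that the item suggested the answer. A low rate could mean that samples were not handed out, or that they were and the letter went unnoticed. These call for different action, and the item cannot tell them apart.

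**Working it through.** **1. The plan's own precision.** The protocol gives no figure for receipt. Its only relevant number is the precision in section 5.7, Table 1. Equation 1 with n = 280 gives a half-width of 1.96 × √[p(1 − p)/280]. At p = 50% this is 5.86 points, and at 60, 70, 80 and 90% it is 5.74, 5.37, 4.69 and 3.51. Table 1 states 5.9, 5.7, 5.4, 4.7 and 3.5, so it reproduces. This interval covers sampling error only.

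**2. Effect of wrong answers.** Let r be true receipt, m the share of recipients who do not answer 'Yes', and f the share of non-recipients who do. Then

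- observed rate = r(1 − m) + (1 − r)f
- bias = (1 − r)f − rm

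The documents give none of r, m or f. All are assumed here, over a range. Entries are the observed rate, with bias in points:

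| r | f | m = 0 | m = 10% | m = 20% |
|---|---|---|---|---|
| 30% | 10% | 37% (+7) | 34% (+4) | 31% (+1) |
| 30% | 20% | 44% (+14) | 41% (+11) | 38% (+8) |
| 50% | 10% | 55% (+5) | 50% (0) | 45% (−5) |
| 50% | 20% | 60% (+10) | 55% (+5) | 50% (0) |
| 70% | 10% | 73% (+3) | 66% (−4) | 59% (−11) |
| 70% | 20% | 76% (+6) | 69% (−1) | 62% (−8) |

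**3. When it exceeds the interval.** With no forgetting, the bias passes the half-width at the observed rate once f is about 8% (r = 30%), 12% (r = 50%) or 17% (r = 70%).

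**4. When the net error is upward.** Bias is positive only if f > mr/(1 − r). With m = 20% this needs f above 0.06/0.70 = 9%, 0.10/0.50 = 20%, or 0.14/0.30 = 47% for r = 30, 50 and 70%.

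**5. Is forgetting realistic?** Patients need a fill within 90 days, but Q8 allows use of the pen for more than a year, so the first prescription that 16A asks about may be well in the past. Setting m to zero is not safe.

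In short, errors of plausible size could exceed the stated precision, in either direction, and the survey holds no item from which f or m could be judged.

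**The case against.** The strongest reply is that the item does what section 4 asks. The research question there concerns recall of the sample that contained the letter, and section 3.1 places the letter in the sample packs. A patient who remembers such a pack and answers 'Yes' has largely given a valid answer; the bracketed sentence identifies the route and may help true recall. The item is also fairly specific (paper copy, named letter, doctor or nurse, first prescription) and offers 'I don't know'.

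Much of this stands. It does not dispose of the point, because the survey never asks whether a sample was given. It supplies the link instead of measuring it, so the share of 'Yes' answers that rest on a remembered sample is unknown. Section 5.6 also lists awareness of the letter separately from receipt, and an inference from the pack is no evidence of awareness.

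Three stronger readings are tempting, and the documents do not support them:

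- *The receipt rate is inflated.* The cue pushes non-recipients towards 'Yes', but forgetting pushes down and neither is quantified. With r = 70%, m = 20% and f = 10% the observed rate is 59%, which is 11 points too low.
- *Section 5.11 says that the error can only be downward.* It names only forgotten receipt as a specific mechanism, but its general reporting-bias caveat has no direction.
- *A true minority could be reported as a majority and change the conclusion on effectiveness.* The majority criterion in section 5.3 concerns the key safety messages, not receipt, and all analyses are descriptive.

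**Conclusion.** The point holds as a modest flaw of measurement. Item 16A contains a suggestive cue on the very thing that it measures, the key treats 'Yes' as correct, and no item on the sample pack lets the reader interpret the answer. The rate of recalled receipt or awareness may be overstated, by an amount that the documents do not allow anyone to estimate. Over the ranges assumed above the error runs from −11 to +14 points, against a half-width of at most 5.9. Those figures illustrate sensitivity and do not predict a bias.

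A reader might hope to correct the rate afterwards. That needs both f and m. For example, with r = 40%, m = 10% and f = 25% the observed rate is 0.36 + 0.15 = 51%. Correcting for f alone gives (0.51 − 0.25)/0.75 = 34.7%; only (0.51 − 0.25)/(1 − 0.10 − 0.25) returns 40%. As neither rate is known, the wording has to be put right before data are collected.

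The effect is confined to a descriptive process measure of dissemination.

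**What to change.** Before launch:

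1. Delete the bracketed sentence from 16A and use two neutral items, each with Yes / No / I don't know: (a) whether the doctor or nurse gave a sample pen pack at the first prescription; (b) whether the patient recalls receiving the paper Patient Information Letter. Neither should mention the link between the two. Item (a) fits best as a short question of its own, since the stem of Q16 is about the letter.
2. Report (b) overall and by (a). This separates no sample given from sample given but letter not recalled. A 'Yes' to (b) with 'No' to (a) would hint at false recall, though both answers are self-reported.
3. Take 16A out of the patient correct-response key.
4. State in section 5.11 that recall error on receipt can run both ways.

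Cost: one extra short item, one cross-table and one sentence in the limitations. The downsides are the loss of a cue that may help true recall and a possibly less favourable receipt rate.

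Two further ideas are not recommended. Showing the letter online but only reading from it by telephone would give the two modes different stimuli, whereas section 5.1 says that both offer the same survey. Estimating f from patients who started before the letter was distributed would need a distribution start date and finer start dates than the bands of Q8; the protocol gives no such date and describes no linkage to pharmacy records.

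### Patient Q16A and Q16B credit only a doctor or nurse, so the reported letter-receipt and counselling rates can be too low when a physician assistant or other practice staff served the patient

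*Protocol*

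**What the plan says.** **Patient survey (Appendix I.3).** Q16A asks the patient to confirm that, at the first prescription, "my doctor or nurse provided me with a paper copy of the Patient Information Letter". Q16B uses the same subject: "My doctor or nurse offered to explain information about the safe use" of the product at first prescription. Both offer Yes, No and I don't know. Q17 then asks: "Other than the information you have received from your doctor or nurse, from what sources have you received and/or accessed information". Its options include a pharmacist and another type of healthcare professional.

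**Who the measures target (Section 3.1).** The Direct Healthcare Professional Communication (DHPC) is to be "distributed to pharmacists and prescribers (endocrinologists and mealtime insulin prescribing primary care physicians, nurse practitioners, and physician's" assistants. The patient letter travels separately, in sample packs that are "routinely provided by HCPs to patients who have been newly prescribed Humalog U-200 KwikPen".

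**What is to be learned (Section 4).** The patient question on the letter is whether the patient recalls receiving the sample that contained it. No provider is named.

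**How non-receipt is read (Section 5.11).** A respondent who reports not having received the communication counts as evidence that dissemination was less than optimal.

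**HCP survey (Appendix I.1).** Q6 lists physician assistant as a role of its own, apart from physician, nurse practitioner and registered nurse. Q20 asks: "Do you or another healthcare professional at your practice discuss the safe use". Q21 uses the same scope for the letter.

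**The concern.** Q16A adds a condition that its research question does not contain: the letter must have come from a doctor or a nurse. Q16B restricts counselling in the same way. Physician assistants are named prescribers in this programme, so some first prescriptions and sample packs can be expected to come from them. A patient served only by a physician assistant, or by other practice staff, who takes the wording literally will answer 'No' or 'I don't know', although the letter was delivered or the explanation offered.

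At stake are two process measures that the protocol plans to report: receipt of the letter and the offer of an explanation at first prescription. Because Section 5.11 turns reported non-receipt into a judgement on dissemination, a 'No' produced by the wording would count against a distribution channel that worked. Section 5.11 names imperfect recall and self-report as limitations, but not this cause.

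**Working it through.** **1. The passages side by side**

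| Place in the protocol | Who is covered |
|---|---|
| Section 3.1, DHPC audience | pharmacists, physicians, nurse practitioners, physician's assistants |
| Section 3.1, sample packs with the letter | healthcare professionals, not further limited |
| Section 4, patient question on the letter | no provider named |
| HCP survey Q20 and Q21 | the respondent or a colleague at the same practice |
| Patient survey Q16A and Q16B | doctor or nurse |
| Patient survey Q17 | sources other than doctor or nurse |

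Nurse practitioners fit under 'nurse'. Physician assistants and other practice staff have no place in Q16A or Q16B. Q17 supports the literal reading, because it places other professionals outside the doctor-or-nurse phrase. It does not repair the gap: it does not mention the letter and is not tied to the first prescription.

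**2. The plan's own precision figure**

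Equation 1 in Section 5.7 with n = 280 gives a half-width of 1.96 × √(p(1 − p)/280). At p = 80% this is 1.96 × √(0.16/280) = 4.7 points, as Table 1 states. The other rows also reproduce: 5.9 points at 50%, 5.7 at 60%, 5.4 at 70% and 3.5 at 90%.

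**3. Size of the shift**

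Observed 'Yes' rate = p × (1 − s × m), where

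- p is the true share of respondents who were given the letter (or offered an explanation) by anyone;
- s is the share of those who were served only by someone other than a doctor or nurse;
- m is the share of that group who answer 'No' or 'I don't know'.

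The protocol gives none of the three, so all values here are assumptions. Other recall error is set aside.

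| p | m | s = 5% | s = 10% | s = 20% | s = 30% |
|---|---|---|---|---|---|
| 60% | 0.5 | 58.5% | 57.0% | 54.0% | 51.0% |
| 60% | 1 | 57.0% | 54.0% | 48.0% | 42.0% |
| 80% | 0.5 | 78.0% | 76.0% | 72.0% | 68.0% |
| 80% | 1 | 76.0% | 72.0% | 64.0% | 56.0% |
| 90% | 0.5 | 87.8% | 85.5% | 81.0% | 76.5% |
| 90% | 1 | 85.5% | 81.0% | 72.0% | 63.0% |

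Example: 80% × (1 − 0.10 × 1) = 72.0%, a shift of −8 points. Over this grid the shift runs from −1.5 points (60%, s = 5%, m = 0.5) to −27 points (90%, s = 30%, m = 1).

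**4. When the shift matches the sampling error**

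With m = 1 the shortfall is p × s. It equals the half-width when s = half-width / p (unrounded half-widths used): 9.6% at p = 60%, 7.7% at 70%, 5.9% at 80% and 3.9% at 90%. With m = 0.5 these shares double. A larger sample narrows the interval but leaves the shift in place.

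**The case against.** **Lay usage.** 'Doctor or nurse' is plain language, and Section 5.1 reports user testing with 9 patients. Many patients may call a physician assistant a doctor or a nurse. This stands as a limit on size: it lowers m, possibly by a lot. It does not remove the gap for patients who read the item literally, and Section 5.1 does not say whether these items were among those tested.

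**Q17 catches the rest.** In part it does. Safe-use information from a pharmacist or another professional is recorded there, so Q16B is not the only trace of counselling. Q17 still cannot show receipt of the letter or an explanation at first prescription.

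**Stronger readings that the protocol does not support.**

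- *A reader might infer that comprehension rates, or the majority criterion in Section 5.3, are biased.* Section 4 lists three patient messages: no dose adjustment between strengths, no transfer to a syringe, and carrying a backup pen. Receipt and counselling are not among them, and correct/incorrect scoring in Section 5.9 applies to questions on the key safety messages. The answer sheet in Appendix I.3 does list 'Yes' as the correct response to Q16A and Q16B, but it is a document mailed to respondents, not a stated scoring rule.
- *A reader might infer that letters handed over by pharmacists are missed.* Pharmacists receive the DHPC, but nothing says that they hand out the sample packs. The point on the letter rests on physician assistants and practice staff.
- *A reader might infer that the HCP survey counts any professional, so that the two surveys will disagree.* Q20 and Q21 stop at the respondent's own practice, which leaves out a pharmacist elsewhere. No comparison between the two surveys is planned either: Section 5.9 lists separate analyses, and Section 8 foresees a report for each group.

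**Conclusion.** The point holds for two process measures. Q16A and Q16B are narrower than the providers described in Section 3.1, and Q16A is narrower than the research question it serves. The effect of the wording runs one way, towards under-reporting of receipt and counselling.

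Its size cannot be derived from the protocol. Under the assumed values it lies between 1.5 and 27 points. At a true rate of 80% it reaches the Table 1 half-width once about 6% of served patients were served only by someone else and all of them deny the item. If few patients saw only a physician assistant or other staff, or if most of them think of that person as a doctor or nurse, the effect is negligible.

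The key-message comprehension rates are not touched, and no threshold is set for receipt or counselling, so no pass/fail conclusion depends on it. This is a minor defect, worth correcting because the correction is cheap and Section 5.11 attaches a conclusion to non-receipt.

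**What to change.** - **Q16A:** ask about receipt from any provider, for example *I was given a paper copy of the Patient Information Letter by my doctor, nurse, physician assistant or other staff at the practice*.
- **Q16B:** change the subject to *my doctor, nurse, physician assistant or another healthcare professional at the practice*. This matches the practice-level scope of HCP Q20 and Q21.
- **Patient correct answer document (Appendix I.3):** make the same change to the two reprinted statements.
- **Q17:** keep the pharmacist and other-professional options, and do not widen the stem so that it excludes them, because the item would then contradict its own list. At most, add *physician assistant* to the stem.

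The cost is a small wording revision to an instrument that has been through user testing (Section 5.1) and IRB approval (Section 6.3), plus the answer sheet. It adds no questions, respondents or analyses. If the items can no longer be changed, add the restriction to the limitations in Section 5.11 and label the two results as receipt from, and explanation offered by, a doctor or nurse.
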